- Prior personal ACS history (known at time of provider interview)
- Previous enrollment in the study
- Traumatic injury to the chest
- Suicidal ideation or active psychosis or behavioral issues requiring psychiatric monitoring
- Hemodynamic instability
- Non-English speaking
- Potential issues affecting follow up
 - Prisoners, homeless patients, out-of-town residences

4. Enrollment/Group Assignment

We will screen patients presenting to the Methodist ED with the chief complaint of chest pain. Sources for this information include the ED tracking systems and electronic medical records systems. Patients will be evaluated with the HEART score by their treating physician to determine if the patient initially qualifies to participate in the study. The treating physician will provide the information necessary to calculate the HEART score. Qualifying subjects will then be approached for final eligibility assessment using the GAD-7 and consented if interested and eligible.

Enrolled subjects will be assigned to either arm depending upon enrollment period. In the 8 weeks prior to the MBSR course commencement all subjects enrolled will be assigned to Arm 2: MBSR. This period will be immediately followed by 8 weeks of enrollment in Arm 1: Standard Referral. To decrease subject bias with regard to the interventional arm, potential enrollees will remain blinded to the enrollment period until informed consent is complete. This method of assignment has been chosen to help maximize intervention enrollment given the limited recruitment period.

5. Study Procedures (see figure 1 for an overview of protocol)

[figure not shown]
Figure 1 illustrates an overview of the flow of screening and enrollment for both specific aims. The patients who screen eligible in Aim 1 are the population of interest for assignment in Aim 2. The goal is to assign 40 subjects for the intervention arms. Each enrolled subject will have follow up evaluations at 45 days, 3 months, 6 months, and 1 year. Two ED physicians will independently review medical records of each enrolled patient for the described outcome variables and adjudicate any discordances by consensus.

Specific Aim 1: To determine the feasibility of employing rapid cardiac risk stratification and psychological screening to identify patients with LRCP-A in the ED for subsequent referral to MBSR.

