 - d. Proportion of enrolled patients who complete the study and follow up evaluations. We aim to show that 70% of those assigned to MBSR will complete at least 6/8 intervention sessions. Additionally, assuming a 10% loss to follow up at each follow up time point we expect to have 65% who have completed all follow up evaluations.
 - e. Time to first follow up PCP or mental health professional visit.
2. The presence of MACE at 45 days as defined by the following diagnostic criteria:
 - a. Any death of an enrolled patient within 45 days of index ED visit.
 - b. Acute myocardial infarction and coronary revascularization as defined in the Third Universal Definition of Myocardial Infarction.[56]
 - c. Electronic medical record (EMR) review to assess intervening significant cardiopulmonary related diagnoses at 45 days.

Specific Aim 2: To determine the effect of an MBSR training program for patients with LRCP-A on mental health (longitudinal GAD-7 scores, quality of life (PROMIS Global Short Form), and ED resource utilization (return ED visits).

Forty subjects who screen positive for LRCP-A using the process outlined above will be assigned to one of two treatment arms. Enrolled subjects will be referred for standard primary care and/or psychiatric referral for therapy using IU Health's existing consult and referral infrastructure (Arm 1) or for therapy sessions using MBSR (Arm 2) [28, 31]. We plan to recruit eligible subjects for assignment in the 40 days prior to the start of each 8-week MBSR class series.

1. **Arm 1: Standard psychiatric referral:** Subjects will be referred for primary care provider (PCP) follow up and/or to psychiatry for further management and treatment of elevated anxiety levels according to standard of care. The treating ED provider will have discretion as to which referral option they believe to be more appropriate for each patient. This will occur using the hospital system's current infrastructure and act as a "time from referral to treatment" control. Thus, we will have a baseline for the average time it would take for an individual referred for evaluation or treatment to be seen. Subjects will receive a standard set of discharge instructions which will discuss anxiety, chest pain, and instructions for follow up with their PCP. For those patients without a PCP, we will provide a list of PCPs with whom they could establish care. Patients will also be given a resource list of mental health professionals with whom they

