could also schedule follow up with if directed by the ED provider. This list will be a custom list provided by our social work colleagues based upon individual patient factors (proximity to residence, insurance status, etc.) which is currently standard practice. We plan to also send a letter or EMR communication to the patient's PCP if they have one alerting them to their participation in the study, their study assignment, and encouraging further evaluation and management of their anxiety symptoms. For those without a PCP at time of enrollment we will query the patient at each follow up time-point for the establishment of primary care and send this letter if they have been able to do so at that time.

2. **Arm 2: MBSR intervention:** In addition to the standard referrals and discharge instructions discussed above, subjects assigned to MBSR will be offered a referral to a local MBSR course. The standard MBSR course meets one day per week for 8 weeks, with sessions being 2.5 hours in duration. A full day retreat (7 hours in length) is offered on a Saturday between sessions 6 and 7. The primary techniques are the "body scan", a noncritical assessment of bodily sensations when directing attention in a deliberate manner from the feet through the head and focused meditation with a special attention to breathing [57]. The full training program is presented in the intervention instruction manual and Table 1 outlines the contents of each weekly session. Our study interventionist will provide several options for the MBSR course (e.g., different days of the week and times of day) from which to choose to maximize convenience. To maximize MBSR availability for this pilot, these blocks will include groups open to non-study participants as well as closed dedicated study groups.

Table 1. Description of Mindfulness-Based Stress Reduction Sessions

Session #	Session Themes	Meditation Exercises	Didactic Teaching	Home Practice

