8	The rest of your life: Making the practice your own	
 ▪ Body scan ▪ MM ▪ Sitting meditation 	
 ▪ Review of the course with an emphasis on daily strategies for maintaining and deepening mindfulness skills ▪ Sharing of participant perspectives on the program; welcoming all comments 	
 ▪ Mindfulness resources handout ▪ Continuing the practice & making it your own ▪ Bringing seamless attention to life

Outcome assessments: The schedule of assessments is shown in Table 2. These assessments will take place in the method most convenient for the patient (telephone, mail, or online REDCap survey completion). These are all methods the PI and his research team are currently using. **The primary outcome of interest will be the mean longitudinal change in GAD-7 scores between intervention groups at each time point.**

Domain	Measure	# of Items	Time Period Investigated				
			ED	45 day	3 mo	6mo	12mo
MACE [†] Risk	HEART Score	5	x				
ACS Risk	PreTest Consult ACS	8	x				
Demographics	Age, Race, Gender, Education etc.	10	x				
Medication Use	Standard Items	2	x	x	x	x	x
Medical Comorbidity	9-Condition Checklist	9	x				
Chest Pain Symptoms	Custom Items and Numeric Rating Scale	5	x				
Somatization	Patient Health Questionnaire (PHQ-15)	15	x	x	x	x	x
Anxiety Severity	Generalized Anxiety Disorder Scale (GAD-7)	7	x	x	x	x	x
Panic	PHQ Panic Scale	5	x	x	x	x	x
Social Anxiety	Mini-SPIN	3	x	x	x	x	x
PTSD	4-Item screen	4	x	x	x	x	x
Depression	Patient Health Questionnaire (PHQ-8)	8	x	x	x	x	x
Cardiac Anxiety	Cardiac Anxiety Questionnaire	18	x	x	x	x	x
Resilience	Brief Resilience Scale	6	x				
Pain Catastrophizing	Pain Catastrophizing Scale	13	x				
Healthcare Utilization (12 mo Pre-ED)	Custom Items	6	x				
Healthcare Utilization (Post-ED assessment)	Custom Items	6		x	x	x	x
Healthcare Related Quality of Life	PROMIS Global Short Form	10	x	x	x	x	x
Life Trauma	Traumatic Life Events Questionnaire	18	x				
MBSR Mechanism of Action	Cognitive and Affective Mindfulness Scale-Revised (CAMS-R)	10	x	x	x	x	x
MBSR Evaluation	Toronto Mindfulness Scale (TMS)	13	x	x	x	x	x

[†]Major Adverse Cardiac Event

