The goals are to collect preliminary data regarding the feasibility and effectiveness of the MBSR referral and approach compared with standard of care referral. Eligibility, recruitment, and retention information will be tabulated. Frequencies and percentages will be summarized by group for categorical variables, and continuous and count variables will be summarized by group using the mean, standard deviation, and range. The primary outcome of interest will be a comparison of the mean change in GAD-7 scores at 3 months using the t-test. Secondary analysis will look at the comparison of mean change in GAD-7 longitudinally using repeated measures ANOVA. The repeated measures ANOVA will compare scores between groups and compare scores over time within groups. Similar analyses will be used for the other efficacy outcomes. The proportion of subjects with a visit, time to first visit, and number of visits will be compared using chi-square, log-rank, and Wilcoxon rank sum tests, respectively. A 5% significance level will be used for all tests.

Because there is minimal published data to guide power calculations in this population for our outcome of interest we have chosen a sample size of 12 for each interventional arm in this pilot study on the basis of feasibility as described by Julious [62]. This sample size of 12 will be increased to 20 per arm to account for an

[name]

estimated 40% drop out rate prior to completion of the MBSR intervention. Thus, the total number of subjects we expect to enroll to the intervention is 40. All subject data will be analyzed on an intention to treat basis.

9. Privacy/Confidentiality Issues

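### The 45-day GAD-7 falls before the end of the MBSR course for every Arm 2 subject but is used as an efficacy time point; whether the 3-month primary is also affected depends on which enrolment window applies

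*Combined protocol and SAP*

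**What the plan says.** Section 4 (Enrollment/Group Assignment) sets the Arm 2 enrolment period: "In the 8 weeks prior to the MBSR course commencement all subjects enrolled will be assigned to Arm 2: MBSR". Section 5, under Specific Aim 2, sets a different one: "We plan to recruit eligible subjects for assignment in the 40 days prior to the start of each 8-week MBSR class series".

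Section 5, Arm 2, describes the course: "The standard MBSR course meets one day per week for 8 weeks, with sessions being 2.5 hours in duration". The retreat adds no week: "A full day retreat (7 hours in length) is offered on a Saturday between sessions 6 and 7".

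Follow-up is the same for both arms: "Each enrolled subject will have follow up evaluations at 45 days, 3 months, 6 months, and 1 year". The columns of Table 2 start at the ED assessment and continue with 45 days and 3, 6 and 12 months. The MACE outcome in Section 5 counts its 45 days from the index ED visit. Nothing ties an assessment to the start or end of the course.

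For the efficacy outcome, Section 5 (Outcome assessments) names the "mean longitudinal change in GAD-7 scores between intervention groups at each time point". Section 8 says: "The primary outcome of interest will be a comparison of the mean change in GAD-7 scores at 3 months using the t-test". It then adds a repeated measures ANOVA of the longitudinal scores that compares the groups, with similar analyses for the other efficacy outcomes.

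**The concern.** The outcome clock starts at the ED visit. The treatment clock starts later, when a course begins after a batch enrolment window. An early assessment can therefore come before much of the treatment has been offered, and how much depends only on the date the subject came to the ED.

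Aim 2 is worded as the effect of the training programme. An assessment in mid-course does not measure the effect of a programme that has been delivered. If the 45-day score is pooled with later scores in a between-group repeated measures effect, it would tend to pull the estimate towards no difference. If the 3-month score has the same problem, it reaches the primary comparison. Estimates from this pilot are meant to inform later work, so readers need to know how much treatment each one reflects.

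**Working it through.** **Plan's own figure.** The documents give no interval from ED visit to course end. The arm size does reproduce: 12 / (1 − 0.40) = 20 per arm, 40 in total. The 20 is used below.

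**Inputs.** Enrolment window w = 56 days (Section 4) or 40 days (Section 5). Eight weekly sessions, so session 8 is 7 × 7 = 49 days after session 1. First follow-up at day 45. Three months is taken as day 91.

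**Assumptions.** GAD-7 is counted from the ED visit, enrolment is uniform over the window, and visits take place on their nominal day.

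**Formulas.** For a subject enrolled d days before session 1:
- session 8 falls on day d + 49;
- sessions offered by day t = min(8, floor((t − d)/7) + 1) if t ≥ d, otherwise 0.

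**Day 45.** Even with d = 0, session 8 is on day 49, after the assessment. Over d = 1 to 56 the sessions offered sum to 7 × (1+2+3+4+5+6) + 3 × 7 = 168, and 168/56 = 3.0. Subjects with d = 46 to 56 have been offered none: 11/56 = 20%. Over d = 1 to 40 the sum is 2 × 1 + 7 × (2+3+4+5+6) + 3 × 7 = 163, and 163/40 = 4.1.

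**Day 91.** Session 8 has not been reached if d + 49 > 91, that is d > 42. Under 56 days this is d = 43 to 56: 14/56 = 25%, or 0.25 × 20 = about 5 subjects. Those with d = 43 to 49 have been offered 7 sessions and those with d = 50 to 56 have been offered 6. Under 40 days the latest session 8 is on day 40 + 49 = 89, so none are affected and the margin is 2 days.

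| | 8-week window | 40-day window |
|---|---|---|
| Session 8, days after ED visit | 49 to 105 | 49 to 89 |
| Mean sessions offered by day 45 | 3.0 | 4.1 |
| Offered none by day 45 | 20% | 0% |
| Past session 8 by day 45 | 0% | 0% |
| Not at session 8 by day 91 | 25% | 0% |

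**Sensitivity of the 3-month share.**
- Three months as 90 to 92 days: 15/56 to 13/56, or 27% to 23%, under 8 weeks; still 0% under 40 days, with a margin of 1 to 3 days.
- Course end counted as 8 full weeks (56 days after session 1), over the same 90 to 92 days: 22/56 to 20/56, or 39% to 36%, under 8 weeks; 6/40 to 4/40, or 15% to 10%, under 40 days.
- The 45-day result does not change under any of these readings.

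**Six months (day 182).** The latest course end on any reading is day 56 + 56 = 112, so this visit follows it by at least 70 days.

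**The case against.** The strongest reply is that the trial compares referral strategies. The working hypothesis in Section 2 concerns early referral, Section 8 compares referral approaches by intention to treat, and Arm 1 serves partly to measure the wait for treatment. For that question the ED visit is a proper starting point and the wait belongs to the strategy. This stands in part: the 45-day contrast is a valid estimate of the early effect of referral, and a reader who called it meaningless would go too far. But Aim 2 is also worded as the effect of the training programme, and nothing labels day 45 as during treatment.

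A reader might infer that the 3-month primary is compromised. The documents do not support that without a condition. The problem exists under the 8-week window and disappears under the 40-day window. Even under 8 weeks, those affected have been offered 6 or 7 sessions, and the plan's own completion target is 6 of 8. At full attendance all can meet it by day 91, although one missed session would put those offered only 6 below it.

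A reader might also infer that the primary must move to 6 months. That is a trade-off, not a correction. It gives up the contrast close to course end, and time since session 8 would still vary by 55 days. At the plan's 10% loss per time point, 20 × 0.9³ = 14.6 per arm would remain, against 20 × 0.9² = 16.2 at 3 months. If the 12 left after the 40% drop-out lost a further 10%, 12 × 0.9 = 10.8 would remain, below the planned 12.

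Finally, the dates are less firm than the arithmetic. The ED anchor for GAD-7 is implied by Table 2, not stated. No visit windows are given, so a late 45-day contact could follow session 8 for the last enrollees. Arm 2 subjects choose among several courses; the examples given are days and times, but individual start dates could differ. These points weaken the exact shares more than the 45-day conclusion.

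**Conclusion.** The 45-day part holds under both stated windows: on the nominal schedule no Arm 2 subject has reached session 8, and on average 3.0 or 4.1 of 8 sessions have been offered. Using this visit as an efficacy time point would tend to dilute a pooled between-group effect. The size cannot be computed, because the plan gives no effect size or SD. The visit-by-visit comparison in Section 5 is not diluted in this way, but its 45-day result needs the right label.

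The 3-month part is conditional: about 25% of Arm 2 (about 5 of 20) under the 8-week window, none under the 40-day window. It follows from two passages that contradict each other and must be reconciled.

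These results rest on the ED-visit anchor, visits on their nominal day and, for the shares and means, uniform accrual. This should be fixed before analysis, but it is not a fatal flaw. It would be tempting to say that visit timing alone makes a null result unreadable. In a pilot sized at 12 per arm on feasibility grounds, a null result could not show that MBSR does not help, whatever the timing.

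**What to change.** 1. In Section 5 and Section 8, label the 45-day self-report scales as a during-treatment (early referral) measure and report them separately. Base the repeated measures group contrast on 3, 6 and 12 months. Day 45 stays in use for MACE, feasibility and description.
2. Reconcile Sections 4 and 5 on the Arm 2 enrolment window so that session 8 falls before the 3-month assessment for every subject, and keep 3 months as primary. The 40-day window already meets this condition (40 + 49 = 89, before day 91). State that GAD-7 follow-up is counted from the ED visit and that course end means session 8, because the margin is only 2 days.
3. Record each Arm 2 subject's session 1 and session 8 dates and tabulate the days from session 8 to each assessment. Interventionist field notes and per-session payments already capture part of this.

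The cost is wording and one table, with no new visit or questionnaire. The 45-day data leave the pooled contrast, and Arm 2 recruitment is 56 − 40 = 16 days, about two weeks, shorter than under the 8-week window. That matters because Section 4 chose its assignment method to maximise intervention enrolment. Moving the primary to 6 months is optional and not required.

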severity and monitor symptom changes and effect of treatment over time. It is comprised of 7 items with an unscored item which assesses patient-rated global impression their symptom related impairment. The scores range from 0-21 with cutpoints at 5, 10, and 15 for mild, moderate, and severe anxiety, respectively. A cutoff of 10 has a sensitivity for generalized anxiety disorder of 89% and specificity of 82% with test-retest reliability of ICC=0.83 [52, 55]. Patients who score ≥ 10 on the GAD-7, indicating at least moderate levels of anxiety, will be eligible for enrollment if their ED provider agrees with the high likelihood of LRCP-A. We plan to delay informed consent until after the GAD-7 determination for practical purposes as having knowledge regarding the study objective may affect the patient's responses the GAD-7. Patients will have opportunity to consent to retain the collected information as well as continue on with the study. For ineligible subjects, we will only retain counts and total scores for feasibility calculations but no identifiable information will be kept. For eligible patients, trained research personnel (investigator, research assistant, or social worker) will discuss the results of the screening tests with the patient and introduce the study and a research assistant or coordinator will obtain informed consent for assignment from interested subjects. Those who enroll will answer questionnaires assessing the domains presented and described further in table 2 below.

Outcome assessments:

1. Protocol feasibility will be assessed via patient eligibility, recruitment, and retention.
 - a. Rate of eligible patients: # of eligible patients per month based on heart score, and the % of those patients who have an eligible GAD-7 score. We believe that 30% of subjects screened will be eligible for enrollment based on prior work.
 - b. Proportion of eligible patients who enroll. Based on prior work with this population in an observational study, our target is 40%.
 - c. Proportion of enrolled patients with an intervention session or follow up visit. We aim to have 75% of those assigned to MBSR complete at least 1 session.

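### The stated blinding ends at consent, before nine repeated baseline scales; the window that sets arm membership is 8 weeks in one section and 40 days in another; and a provider condition is missing from the entry criteria

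*Combined protocol and SAP*

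**What the plan says.** **Assignment.** Section 4 (Enrollment/Group Assignment) sets the arm by calendar period: "In the 8 weeks prior to the MBSR course commencement all subjects enrolled will be assigned to Arm 2: MBSR". It continues: "This period will be immediately followed by 8 weeks of enrollment in Arm 1: Standard Referral". The reason given is to maximise enrolment in the intervention within a short recruitment period.

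**Blinding.** The only blinding statement, also in Section 4, is that "potential enrollees will remain blinded to the enrollment period until informed consent is complete".

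**Order of baseline measures.** Section 5 (Specific Aim 1) takes the GAD-7 before consent because "having knowledge regarding the study objective may affect" the patient's answers to it. It then says: "Those who enroll will answer questionnaires assessing the domains presented and described further in table 2 below". Table 2 lists those measures.

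**Provider condition.** The same part of Section 5 says that patients scoring 10 or more on the GAD-7 "will be eligible for enrollment if their ED provider agrees with the high likelihood of LRCP-A". Neither list in Section 3 (Inclusion/Exclusion Criteria) contains this condition. For ineligible subjects, "we will only retain counts and total scores for feasibility calculations".

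**Second window.** Section 5 (Specific Aim 2) states: "We plan to recruit eligible subjects for assignment in the 40 days prior to the start of each 8-week MBSR class series".

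**Primary analysis.** Section 8 compares mean GAD-7 change at 3 months by t-test, and applies similar analyses to the other efficacy outcomes.

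**The concern.** Because a whole period belongs to one arm, a subject who knows the period knows the arm. The plan keeps this from patients up to consent and states no protection afterwards, although most self-report baselines are collected after that point. If subjects do know their arm when they answer, change from baseline on those scales could differ between arms for reasons unrelated to the intervention. PROMIS is a named Aim 2 outcome, and CAMS-R and TMS are used in Section 5 to judge whether the intervention was received and enacted.

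The window matters for two reasons. It decides who belongs to which arm, and it decides how long an MBSR subject may wait for the course and so how much of it comes before the 3-month visit.

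The provider condition matters because it is a judgement on entry. The text does not say that it is made without knowledge of the open period. It also leaves unclear whether a patient whom the provider declines counts as eligible in the Aim 1 feasibility rates.

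**Working it through.** **1. The plan's own figure.** Section 8 inflates 12 per arm for 40% drop-out: 12 / (1 − 0.40) = 20 per arm, 40 in total. This reproduces and is not affected by the point.

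**2. Scales collected after the stated blinding ends (Table 2).**
- All ED-column items: 5+8+10+2+9+5+15+7+5+3+4+8+18+6+13+6+10+18+10+13 = 175. These include items that are not self-report, such as the HEART score.
- Scales at the ED visit and at every follow-up, other than GAD-7: PHQ-15 15, panic 5, Mini-SPIN 3, PTSD 4, PHQ-8 8, cardiac anxiety 18, PROMIS 10, CAMS-R 10, TMS 13. The sum is 86.
- So nine of the ten repeated scales fall after consent. The tenth, GAD-7, falls before it.

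**3. The windows.** 8 weeks = 56 days, and 56 − 40 = 16 days. Section 4 describes one Arm 2 period followed by one Arm 1 period. Section 5 speaks of each class series and names no arm. The visible text does not give the number of blocks per arm.

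**4. Illustration: how much of the course precedes the 3-month visit.** The assumptions are mine:
- visits count from the index ED visit, as Section 5 does for deaths within 45 days;
- enrolment is even over the window;
- there is one start date;
- 3 months is day 91, with 89 to 92 as a range.

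Sessions are weekly (Section 5, Arm 2), so session 8 is 7 × 7 = 49 days after session 1. Let W be the window, s the days from the start date to session 8, and m the visit day. The share seen before session 8 is max(0, W − (m − s)) / W. Table 1 lists an orientation before session 1 without a date, so s is either 49 (session 1 on the start date) or 56 (start date is an orientation one week before session 1).

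| Start date is | Window | Latest session 8 | Share at day 91 | Day 89 / day 92 |
|---|---|---|---|---|
| Session 1 | 40 days | 40+49 = day 89 | 0% | 0% / 0% |
| Session 1 | 56 days | 56+49 = day 105 | (56−42)/56 = 25.0%, 5 of 20 | 28.6% / 23.2% |
| Orientation | 40 days | 40+56 = day 96 | (40−35)/40 = 12.5% | 17.5% / 10.0% |
| Orientation | 56 days | 56+56 = day 112 | (56−35)/56 = 37.5% | 41.1% / 35.7% |

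The plan's completion target is 6 of 8 sessions, and session 6 is 35 days after session 1. With session 1 on the start date, the latest session 6 is day 40+35 = 75 or 56+35 = 91, so all could have reached it by day 91 under either window. With the orientation start it is day 82 or day 98, and under 8 weeks (56−49)/56 = 12.5% would be seen before it.

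**5. The provider condition.** The documents give no figure from which to size selection through it.

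**The case against.** The blinding point is drawn from silence. Section 4 says when blinding may end, not when the arm is disclosed, and Section 5 does not place disclosure before or after the questionnaires. Figure 1 is not shown in the text available to this review and may give the order. This stands. A reader might infer that subjects do learn their arm before answering, or that the primary comparison starts from a compromised baseline. The documents support neither, and the GAD-7 is taken inside the blinded phase.

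A reader might also take the plan's reason for delaying consent as its own admission of the problem. That reason concerns knowledge of the study objective, which subjects in both arms have after consent. It supports a concern about knowledge of the arm only by analogy.

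The timing figures are fragile. The 0% under 40 days rests on a two-day margin (day 89 against day 91) and disappears if an orientation comes first. Section 5 offers several course options, so start dates may differ. Analysis is by intention to treat, and no text requires the course to be finished by 3 months. It would therefore be wrong to conclude that a quarter of the MBSR arm will be assessed too early.

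On the windows, one could read the 40 days as the part of the 8 weeks in which recruitment takes place. Section 4 does not say so. It assigns everyone enrolled in the 8 weeks to MBSR, and Section 5 does not restrict the 40 days to one arm.

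Finally, assignment by period is stated openly with its reason, and Section 8 calls the goals preliminary. That is fair, and the point does not ask for a different design.

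**Conclusion.** The point holds as a gap in wording and two inconsistencies.

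- **Blinding.** The visible text gives no protection from knowledge of the arm for nine repeated baseline scales (86 of 175 ED-column items). The exposure is possible, not shown, and is limited to secondary scales. Its size and direction cannot be estimated.
- **Windows.** The 8-week and 40-day statements differ by 16 days on a rule that sets arm membership, and they need reconciling whatever their effect. The shares before session 8 (0% against 25%, or 12.5% against 37.5%) only illustrate that the choice also affects the primary visit. They depend on the assumptions listed above.
- **Provider condition.** Its absence from Section 3 is an inconsistency on its face. A reader might infer that providers select patients by period; the documents show only that nothing stated prevents it.

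The changes are worth making because they are cheap and because the pilot's products, feasibility rates and preliminary estimates, rest on these definitions. Confidence is medium.

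**What to change.** - **(a) Blinding, Section 4.** Move the end of blinding from completion of consent to a later point: subjects are not told the enrolment period or arm until consent is complete and the ED self-report scales in Table 2 are finished, or the subject stops answering. At minimum this should cover the nine repeated scales, asked first. Cost: the arm is disclosed somewhat later in the ED visit.
- **(b) Windows, Sections 4 and 5.** Reconcile the 8-week and 40-day statements, say which arm each applies to, and give the number of blocks per arm. Cost: wording only.
- **(c) Provider condition, Sections 3 and 5.** Reconcile the two sections. Record the provider's judgement before consent, and count non-agreement by enrolment period. Cost: a small new data item. Section 5 keeps counts and total scores for ineligible subjects but does not say that they are split by reason or period. Keeping the period from providers in a single ED may be imperfect.
- **(d) Optional, Section 8.** Describe the Aim 2 results as preliminary estimates from a non-randomised, period-assigned comparison, as Sections 4 and 8 largely imply. Cost: wording only.

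The 20 per arm and assignment by period stay as they are.
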